4.2 EXPLORATORY ENDPOINTS

- Proportion of subjects with a mean Hb level within 10-12 g/dL from Week 16 to Week 24
- Proportion of subjects with Hb > 12 g/dL any time during treatment
- Proportion of subjects with Hb > 13 g/dL any time during treatment
- Percentage of time with Hb, values within 10.0 to 12.0 g/dL from Week 16 to Week 24
- Time to first RBC transfusion
- Proportion of subjects with a mean Hb level ≥ 10 g/dL in the first 8 weeks after conversion or initiation of treatment
- Proportion of subjects with a mean Hb level ≥ 10 g/dL (averaged from Week 16 to Week 24) based on baseline ESA use status ≥ 6 weeks (conversion from ESA to roxadustat based on prior ESA use) and < 6 weeks (initiation of roxadustat based on body weight)
- Evaluate the utilization of IV iron (IV iron use/4 weeks)

- Evaluate the effect on iron indices
- Evaluate dosing adherence
- Conversion subjects: Comparison of starting dose of roxadustat to roxadustat dose at Weeks 16 to 24
- Mean number of dose adjustments (including dose-hold) during study
- Proportion of subjects requiring blood/pRBC transfusion from Week 5 (Day 29) to Week 24/ET.
- Proportion of subjects requiring rescue therapy (blood/pRBC transfusion or ESA rescue) from Week 5 (Day 29) to Week 24/ET

In addition to the exploratory endpoints in the protocol, additional exploratory efficacy endpoints of interest are presented in this section.

RBC transfusion data is collected in the Blood Transfusions form of the eCRF.

For efficacy evaluation, Hb values will be censored for 4 weeks if blood/pRBC is administered during the treatment period. Hb results obtained from the central laboratory will be used to determine the Hb response.

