5 GENERAL STATISTICAL CONSIDERATIONS

5.1 STATISTICAL METHODOLOGY

Safety and efficacy data will be summarized and presented by time points in summary tables. Continuous variables will be presented by descriptive statistics: n, mean, standard deviation, median, minimum, and maximum. Categorical variables will be tabulated by frequency counts and percentages.

Lab results obtained from the central laboratory, rather than local laboratories, will be used for all efficacy and safety analyses. Local laboratory values, if collected in the eCRFs, will only be presented as data listings.

Unless otherwise stated, all confidence intervals will be two-sided 95% confidence intervals.

All analyses will be performed using SAS® Version 9.4 or higher.

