5.2 SAMPLE SIZE DETERMINATION

Approximately 300 subjects with anemia of CKD (either with or without prior treatment with an ESA before enrollment) and on hemodialysis are planned in this study. This number of subjects distributed across the specified number of sites is adequate to evaluate the primary study objective.

Assuming the proportion of subjects that maintain Hb levels ≥ 10 g/dL from Weeks 16 to 24 is at least 80%, with a sample size of 300, the study will be able to produce a two-sided 95% confidence interval (CI) with a width equal to 9.5%.

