5.3.2 Full Analysis Set (FAS)

The FAS set will consist of all subjects who signed the informed consent, were enrolled, and provided baseline Hb data and data for at least one post baseline Hb time point. The FAS set will be used for all efficacy endpoints.

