6 SUBJECT ACCOUNTABILITY AND DISPOSITION

The following subject data will be summarized and presented if applicable, by number and percentage:

- Subjects enrolled at each center, and for all centers combined (using the enrolled population)
- Subjects in each analysis set (using the enrolled population)
- Subjects who prematurely discontinued during the treatment period, and by discontinuation reason for the enrolled population.
- Subjects who complete the treatment period (will be considered as “completers”)
- Subjects who participated in the Post-treatment Follow-Up
- Subjects who completed the EOS Visit
- Subjects who entered extension study

Kaplan-Meier plots will be generated for premature treatment discontinuations showing one curve.

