9.2 ANALYSIS OF EXPLORATORY ENDPOINTS

The analysis for the exploratory endpoints will be based on the FAS population.

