9.2.8 Blood Transfusion and ESA Usage as Rescue Therapy

Blood/pRBC transfusions will be recorded in the Blood Transfusion Form of the eCRF. ESA, as rescue therapy, will be recorded in the Concomitant Medication eCRF.

The following 2 endpoints will be analyzed:

- Proportion of patients requiring a blood/pRBC transfusion from Week 5 (Day 29) to Week 24/ET. The 95% CI of the response rate will be presented based on normal approximation.
- Proportion of patients requiring rescue therapy (blood/pRBC transfusion or ESA rescue) from Week 5 (Day 29) to Week 24/ET. The 95% CI of the response rate will be presented based on normal approximation.

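### The exploratory rescue composite is a crude FAS proportion from Day 29 with no allowance for subjects who leave, so read as a Day 29 to Week 24 risk it tends to be too low

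*SAP*

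**What the plan says.** SAP 4.2 lists the composite last among its exploratory endpoints: "Proportion of subjects requiring rescue therapy (blood/pRBC transfusion or ESA rescue) from Week 5 (Day 29) to Week 24/ET". SAP 9.2.8 repeats it as "Proportion of patients requiring rescue therapy (blood/pRBC transfusion or ESA rescue) from Week 5 (Day 29) to Week 24/ET", together with the same proportion for transfusion alone. The only analysis instruction given for each is this: "The 95% CI of the response rate will be presented based on normal approximation". Section 9.2.8 names no denominator, no risk set at Day 29 and no rule for subjects who leave.

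The denominator comes from SAP 9.2: "The analysis for the exploratory endpoints will be based on the FAS population". SAP 5.3.2 defines the FAS as enrolled, consented subjects who "provided baseline Hb data and data for at least one post baseline Hb time point". SAP Table 5 sets the Week 2 window at Days 2 to 21, so a subject can qualify more than a week before Day 29. Protocol 5.4 says that leavers are not replaced.

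Other parts of the SAP do allow for unequal follow-up. Section 9.2.1 gives a Kaplan-Meier proportion for first RBC transfusion, counted from first dose. Section 10.1.1 gives exposure-adjusted as well as crude adverse event rates. Section 6 gives a Kaplan-Meier plot of premature discontinuation and tabulates "Subjects who prematurely discontinued during the treatment period, and by discontinuation reason for the enrolled population". None of these covers ESA rescue or the composite.

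**The concern.** The event window and the denominator do not match. Events count only from Day 29 until Week 24 or early termination, but the denominator includes everyone who entered the FAS from Day 2 onwards. Two groups are scored as rescue-free without having been observed as such: those gone before Day 29, and those who left between Day 29 and Week 24.

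The composite is the one listed endpoint in which ESA rescue counts as a failure. SAP 4.2 sets aside haemoglobin values for 4 weeks after blood or pRBC but states no such rule for ESA. A reader who wants to know how often roxadustat had to be supplemented will therefore look at this figure and is likely to read it as a risk over the stated window. Dropout pulls that reading in one direction, and a larger sample does not remove the effect. Protocol 5.3 also lists lack of efficacy, or meeting the ESA withdrawal criteria, as a reason for stopping, so some exits may be closely tied to the need for rescue.

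**Working it through.** SAP 9.2.8 states no rate, so there is no figure of the plan's to reproduce. The 9.5% interval width in SAP 5.2 concerns the haemoglobin responder rate and has no bearing here.

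**Inputs from the documents**
- Planned size (SAP 5.2): "Approximately 300 subjects with anemia of CKD".
- Interval (SAP 5.1): "Unless otherwise stated, all confidence intervals will be two-sided 95% confidence intervals".
- Counting window: Day 29 to Day 168 (24 × 7), which is 140 days after the first 28.

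**Assumed inputs (not in the documents)**
- Risk R of rescue from Day 29 to Day 168 under full follow-up: 10%, with 5% to 20% as a range.
- Dropout D by Day 168: 10%, 20% or 30%.
- Constant hazards, and exit unrelated to rescue need in the base case.

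**Direction.** The numerator contains only the observed events, a subset of all events that would occur by Week 24. The denominator is at least as large as the group at risk on Day 29. The crude ratio therefore cannot exceed the risk.

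**Formula.** Dropout hazard a = −ln(1−D)/168. Rescue hazard b = −ln(1−R)/140.

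Crude FAS proportion = exp(−28a) × b/(a+b) × [1 − exp(−140(a+b))]

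The same expression without the factor exp(−28a) is the crude proportion among subjects still present at Day 29.

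**Worked case, R = 10%, D = 20%.** a = 0.2231/168 = 0.001328 and b = 0.1054/140 = 0.000753. The three factors are 0.9635, 0.3617 and 0.2527, and their product is 0.0881.

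| Dropout | Gone before Day 29 | Crude, whole FAS | Crude, present at Day 29 | Risk | Relative shortfall (whole FAS) |
|---|---|---|---|---|---|
| 10% | 1.7% | 9.4% | 9.6% | 10.0% | 6% |
| 20% | 3.7% | 8.8% | 9.1% | 10.0% | 12% |
| 30% | 5.8% | 8.2% | 8.7% | 10.0% | 18% |

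The relative shortfall is nearly the same for risks from 5% (crude 4.7%, 4.4%, 4.1%) to 20% (18.8%, 17.6%, 16.4%).

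**A different dropout pattern.** With exit times uniform over 168 days, crude = (1−D)R + D × (1/168)[140 − R/b]. At R = 10% the bracket divided by 168 is 0.0424, which gives 9.42%, 8.85% and 8.27%. The answer hardly depends on the dropout model.

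**A limit of the model.** It keeps every early leaver in the FAS. Those who leave with no post-baseline haemoglobin are in fact excluded, so the planned figure lies between the whole-FAS column and the present-at-Day-29 column.

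**Exit related to rescue need.** Let leavers' later rescue hazard be k times the on-study hazard. At R = 10% and D = 20% the crude figure stays at 8.8%, while the true risk is:

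| k | 0 | 0.5 | 1 | 2 | 3 |
|---|---|---|---|---|---|
| True risk | 8.8% | 9.4% | 10.0% | 11.1% | 12.1% |

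**Against sampling error.** At 10% and n = 300 the half-width is 1.96 × √(0.10 × 0.90/300) = 3.4 points. The base-case shortfall of 0.6 to 1.8 points lies within it.

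**The case against.** The strongest reply is that the SAP claims no full-follow-up risk. Its window ends at early termination, and as a count of FAS subjects rescued on study after Day 28 the crude proportion is correct. Rescue is also hard to define after exit: protocol 4.7.3.2 ties ESA rescue to the Treatment Period, and protocol 4.6 foresees subjects who stop roxadustat going on to an ESA, which is then ordinary care. A risk that runs past exit is therefore a different and partly hypothetical quantity. This stands, and it is why the point is limited to how the figure will be read and why the crude count should stay.

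It also stands that the size rests on assumed rates, that it is smaller than the sampling error, that SAP 9.2.1 already covers transfusion, and that the whole-FAS denominator follows from SAP 9.2 and is not written in 9.2.8.

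A reader might go further and infer three things that the documents do not support.

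- That this is the plan's main measure of treatment failure. It is the last of 14 exploratory endpoints in SAP 4.2, it is absent from the exploratory list in protocol 3.2.2, and SAP 11 says that no hypothesis is tested.
- That the distortion always favours roxadustat. It is nil when leavers would have had no later rescue need, as after death.
- That plain Kaplan-Meier is the correction. Death and kidney transplant are listed exits in protocol 5.3 and are competing events. Censoring them would overstate cumulative rescue. Kaplan-Meier also does not correct for exits that are themselves due to lack of efficacy.

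**Conclusion.** The point holds in a limited form. As written, SAP 9.2.8 yields a crude proportion whose denominator includes subjects with no chance of a counted event and whose part-way leavers count as full non-events. As a Day 29 to Week 24 risk it never overstates and usually understates. The 6% to 18% relative shortfall rests on the assumed dropout and on exit being unrelated to rescue need. It grows if leavers were more likely to need rescue and vanishes if they were not going to need it at all. The composite is the real gap, because it alone has no analysis that allows for follow-up. The consequence is a possibly flattering descriptive figure in a single-arm study. The haemoglobin endpoints are untouched.

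**What to change.** In SAP 9.2.8:

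1. Define the denominator of both proportions as FAS subjects still under observation in the treatment period at Day 29, and report how many left earlier.
2. For the composite, add the cumulative incidence of first rescue from Day 29 to Week 24 with a 95% interval. Treat death and kidney transplant as competing events and other exits as censored. Keep the crude count beside it.
3. Report the number and timing of exits for lack of efficacy or for meeting the ESA withdrawal criteria next to the estimate, because that censoring may be informative.

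Step 1 alone closes only part of the gap: at a 10% risk and 20% dropout it moves 8.8% to 9.1%. With step 2 the estimate would lie between 9.1% (all exits competing) and 10.0% (all exits censored).

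The cost is a few sentences and one added analysis on data already collected. The reported rescue figure becomes slightly less favourable.

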9.3 SUBGROUP ANALYSIS

Primary efficacy endpoints will be presented by forest plots based on the following subgroups: sex, age group, baseline Hb categories, baseline iron status, cardiovascular/cerebrovascular/thromboembolic medical history, starting dose, participating dialysis organizations, and baseline ESA dose categories. Overall summary of TEAEs will be analyzed by subgroups of starting doses of roxadustat.

Other endpoints of interest may be analyzed by the subgroups listed above as needed.

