2.6. Roxadustat Dose Rationale

The starting roxadustat doses and dose titration algorithm in this study are based on Phase 3 program involving ESRD patients with anemia who converted to roxadustat from stable ESA and patients who never used ESA before. These dosing schedules effectively corrected anemia and or maintained Hb levels close to 11.0 g/dL.

Analysis of the Hb time course after initiation of treatment with roxadustat in patients previously not on ESA treatment stratified by body weight indicated that the starting doses for patients not previously receiving ESA treatment should be 70 mg for patients with a body weight of <100 kg, and

Confidential Page 27 of 69

Protocol FGCL-4592-096 A01

Roxadustat 100 mg for patients with a body weight of ≥100kg. The proposed dose adjustment algorithm, applied

every 4 weeks, effectively maintained Hb levels close to 11.0 g/dL in these patients. For patients previously treated with an ESA, the applied starting doses of roxadustat (based on the

conversion table) in conjunction with the dose adjustment algorithm resulted in Hb levels that were maintained close to 11.0 g/dL. The full dose range of 20 to 400 mg TIW was utilized in the Phase 3 dialysis studies.

In this study, the initial dose of roxadustat will be determined by the subject's average prescribed ESA dose in the last 4 weeks prior to enrollment if on epoetin or darbepoetin (8 weeks if on Mircera®).

Using the conversion table (Table 1), in this study, subjects will receive starting roxadustat doses of 70 mg, 100 mg, 150 mg, or 200 mg. If the converted initial dose exceeds the maximum dose of 3.0 mg/kg/dose then the lower dose step should be chosen as the initial dose. Roxadustat doses will be administered at a frequency of TIW. If a subject requires < 20 mg TIW (i.e., < 60 mg per week) to maintain a Hb level of 11±1 g/dL, the dosing frequency should be reduced in a step-wise fashion e.g. TIW to BIW, BIW to QW, QW to Q-2 Week etc.

2.6.1. **Maximum Dose for Roxadustat**

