3. OBJECTIVES AND ENDPOINTS

3.1. Objectives

3.1.1. Primary Objectives

To confirm safe and effective Roxadustat dosing regimens among in-center HD subjects converted from ESA therapy (>=6 weeks ESA treatment) or who are ESA-naïve (<6 weeks ESA treatment).

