2 STUDY DESIGN

[figure not shown]
This open-label single arm study is designed to evaluate roxadustat in maintaining hemoglobin (Hb) in ESRD subjects receiving in-center hemodialysis either after conversion from a stable ESA dose: ESA use \geq 6 weeks prior to conversion to roxadustat dosing or as initial anemia treatment, in subjects with < 6 weeks of total ESA use prior to start of roxadustat dosing.

The study periods are as follows:

- **Screening Period:** Up to 6 weeks
- **Treatment Period:** 24 weeks
- **Post-Treatment Follow-Up Period:** Subjects permanently discontinuing roxadustat, should have one final safety assessment (Treatment Emergent Adverse Events (TEAEs) and Treatment Emergent Serious Adverse Events (TESAEs)) 28 days after the last roxadustat dose.

An extension of roxadustat treatment after 24 weeks may be offered to interested subjects within the context of the study protocol upon agreement with the study site. Data listings for the extension phase will be generated upon database lock and will include serious adverse events (SAEs), concomitant medications related to SAEs, and hospitalization records related to SAEs.

Study Design Overview

Primary Efficacy Endpoint: • Proportion of subjects with mean Hb \geq 10.0 g/dL, averaged over weeks 16-24

Secondary Efficacy Endpoints: • Proportion of subjects with mean Hb between 10-12 g/dL, averaged from week 16 through week 24

Conversion subjects:

- Mean Hb change from baseline to average Hb from week 16-24

Subjects will be dosed three times weekly (TIW), except if a subject requires < 60 mg/week to maintain Hb levels, in which case dose frequency may be reduced in a stepwise fashion, e.g., to twice weekly (BIW), then once weekly (QW).

Initial Dose

Conversion from ESA to Roxadustat

The initial roxadustat dose is determined using a conversion table based on the subject's previous prescribed ESA dose in the last 4 weeks prior to enrollment (for Mircera®:in the last 8 weeks prior to enrollment) (Table 1.1).

Roxadustat treatment should start after the following intervals:

- Two days after stopping epoetin
- One week after stopping darbepoetin alfa
- Two weeks after stopping methoxy polyethylene glycol-epoetin beta (Mircera®)

If the converted initial dose exceeds the maximum dose of 3.0 mg/kg/dose then the next-lower dose step should be chosen as the initial dose.

Table 1.1. Conversion from ESA to Roxadustat

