Previous dose of Darbepoetin alfa (mcg/week)	Previous Dose of Epoetin alfa (IU/week)	Previous Dose of Mircera® (mcg/month)	Starting Dose of Roxadustat (mg/dose TIW)
<25	<5000	<80	70
25 to 40	5000 to 8000	80 to 120	100
>40	>8000	>120	150

Initiation of Roxadustat Dosing in Subjects with < 6 weeks of Prior ESA or No Prior ESA Use

The initial roxadustat dosing is based on broad body weight categories (estimated dry weight at enrollment) as described in Table 1.2.

Table 1.2. Initial Roxadustat Dosing

Body Weight Category	< 100 kg	≥ 100 kg
Roxadustat Dose (TIW)	70 mg	100 mg

Note: Weight in HD subjects = subject's estimated dry weight at enrollment.

Dose Adjustments

During the treatment period, roxadustat dose adjustments will be made starting at Week 4 and at intervals of every 4 weeks thereafter according to the dose adjustment algorithm in [Table 1.3](#), in order to achieve an Hb level of 11 g/dL and maintain an Hb of 11±1 g/ dL. Any potential dose escalation/dose reduction will be at pre-defined dose step increments.

Table 1.3. Roxadustat Dose Adjustment Rules

		Current Hb level:			
		<10.5 g/dL	10.5 to 11.9 g/dL	12.0 to 12.9 g/dL	>13.0 g/dL
6 .. 5 .. 4 .. 3 .. 2 .. 1 .. 0 ..	> 1.0 g/dL	No change	↑	↓	
 ▪ Hold dosing ▪ Check Hb and resume dosing when Hb < 12.0 g/dL, at a dose reduced by 2 steps
	-1.0 g/dL to +1.0 g/dL	↑	No change	↓	
	<-1.0 g/dL	↑	↑	No change*	

F: Increase dose by one step; ! : reduce dose by one step.

• continue to hold dose

Notes:

Dose Increases and Reductions

- Dose increases (↑) and reductions (↓) are preset.
- The dose steps are as follows: 20, 40, 50, 70, 100, 200, 250, 300, and 400 mg.
- If <20 mg/dose is required, dosing frequency should be reduced in a step-wise fashion e.g., TIW to BIW, BIW to QW.
- The maximum dose is capped at 400 mg or 3.0 mg/kg/dose (whichever is lower). Rounding the mg/kg calculated roxadustat dose up to 10 mg may be allowed, if no safety concerns.

Roxadustat dose adjustment reviews should occur every 4 weeks however, a dose reduction may be implemented at any time if the following criteria are met:

- Rate of Hb rise > 2 g/dL within 4 weeks: reduce dose by 1 dose step
- Hb level 13 g/dL: hold dose, until Hb drops to < 12 g/dL, resume dosing at 2 dose steps lower

Any dose adjustment will reset the dose-adjustment window to every 4 weeks thereafter (e.g., dose adjustment for a qualified reason at Week 6 leads to next dose adjustment at Week 10).

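### SAP 9.3's starting-dose subgroup pools converters and initiators at 70 mg and 100 mg, so differences across doses can reflect cohort mix; for TEAEs no ESA-status split is specified

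*SAP*

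**What the plan says.** SAP 9.3 lists the forest-plot subgroups for the primary endpoint and then adds one subgroup for safety. The list ends, and the safety sentence follows, with "starting dose, participating dialysis organizations, and baseline ESA dose categories. Overall summary of TEAEs will be analyzed by subgroups of starting doses of roxadustat". ESA status is not among the subgroups.

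Two rules set the starting dose (SAP section 2; Protocol 4.5.3):

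- **Conversion (ESA use of 6 weeks or more).** "The initial roxadustat dose is determined using a conversion table based on the subject's previous prescribed ESA dose". Table 1.1 gives 70, 100 or 150 mg three times weekly. A dose above 3.0 mg/kg is replaced by the next-lower step.
- **Initiation (less than 6 weeks of ESA, or none).** The dose depends on estimated dry weight (Table 1.2). Protocol 2.6 gives the reason: the "starting doses for patients not previously receiving ESA treatment should be 70 mg for patients with a body weight of <100 kg", and 100 mg at 100 kg or more.

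The cohorts also enter on different Hb criteria (Protocol 5.1): 9.0 to 12.0 g/dL for converters and below 10.0 g/dL for initiators. Response means an average Hb of at least 10 g/dL over Weeks 16 to 24.

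The primary objective in Protocol 3.1.1 is "To confirm safe and effective Roxadustat dosing regimens among in-center HD subjects converted from ESA therapy", and the sentence goes on to include ESA-naïve subjects.

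**The concern.** The primary objective concerns dosing regimens within each cohort. A regimen here is a cohort with its own starting rule, not a tablet strength. The two cohorts meet at 70 mg and at 100 mg, in proportions that nobody fixes: there is no stratification and no planned split of the roughly 300 subjects.

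Every initiator screens below the response threshold, whereas a converter may already be above it. The cohorts could therefore plausibly differ in response, and they could differ in adverse events. If they do, a low response or a high TEAE rate at 70 mg could be read as a fault of that starting dose when it reflects a larger share of initiators. Conversely, a regimen that performs poorly could be masked by the other regimen at the same dose.

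**Working it through.** The plan gives no figure on this point, so there is none to reproduce. The check has two parts.

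**1. Which regimens feed which level (SAP Tables 1.1 and 1.2)**

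| Starting dose | Converters | Initiators |
|---|---|---|
| 70 mg | lowest ESA row | under 100 kg |
| 100 mg | middle ESA row, plus top-row subjects moved down by the cap | 100 kg or more |
| 150 mg | top ESA row | none |

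The cap matters only at the edge of the eligible range. A dose of 150 mg exceeds 3.0 mg/kg when weight is below 150 / 3.0 = 50 kg, and entry weight starts at 45 kg.

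**2. How large a case-mix gap can be**

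The documents give N = 300. The rest is assumed: initiator share s, converters spread evenly over three rows, 80% of initiators under 100 kg, response 85% in converters and r in initiators, both constant across doses. Any trend across doses is then case mix by construction.

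With I = 300s initiators and c = 300(1 − s)/3 converters per row:

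- Response at 70 mg = (0.85c + 0.8I·r) / (c + 0.8I)
- Response at 100 mg = (0.85c + 0.2I·r) / (c + 0.2I)
- Response at 150 mg = 0.85
- Gap, 150 minus 70 mg = (initiator share at 70 mg) × (0.85 − r)

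For s = 0.2 and r = 0.65, I = 60 and c = 80:

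- 70 mg: (68 + 31.2) / 128 = 77.5%
- 100 mg: (68 + 7.8) / 92 = 82.4%
- 150 mg: 85.0%
- Gap: 48/128 × 20 = 37.5% × 20 = 7.5 points

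Other cases, by the same formula:

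| s | r | Initiator share at 70 mg | Gap (points) |
|---|---|---|---|
| 0.1 | 0.75 | 24/114 = 21.1% | 2.1 |
| 0.1 | 0.65 | 21.1% | 4.2 |
| 0.4 | 0.65 | 96/156 = 61.5% | 12.3 |
| 0.4 | 0.55 | 61.5% | 18.5 |

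If both cohorts respond equally, the gap is zero. If initiators respond better, it reverses: with converters at 75%, initiators at 85% and s = 0.2, the three levels read 78.8%, 76.3% and 75.0%. The same mixing applies to TEAE incidence.

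**Comparison with the proposed display.** In the 7.5-point case, five cells would read 85/85/85% for conversion and 65/65% for initiation, with no trend within either cohort.

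**The case against.** A reader might infer that 9.3 splits the primary endpoint by dose only, so that no planned analysis informs any single 70 or 100 mg regimen. The documents do not support that. SAP 9.3 also lists baseline ESA dose categories. In Table 3, Medium matches the 100 mg conversion row for darbepoetin and Mircera and differs for epoetin only at 8000 IU/week. High plus Very High approximates the 150 mg row. SAP 9.2.2 gives the primary proportion by ESA status, and 9.3 plots it by baseline Hb category. For efficacy, much of what is needed to interpret the dose rows is there. The remaining gap is narrower: none of these isolates either initiation row, the Low category starts at 0, and the ESA-status split is not crossed with dose.

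A reader might also infer that the plan will produce a misleading dose trend. That is unsupported too. No document gives an initiator deficit. Protocol 2.6 says that Hb was held close to 11.0 g/dL in both kinds of patient, and dose reviews at Weeks 4, 8 and 12 precede the endpoint window. The displays are descriptive: SAP 11 says no hypothesis is tested, and 9.3 does not call the subgroup a dose-response. In the 7.5-point case, the 95% half-width of the difference is 1.96 × √(0.775 × 0.225/128 + 0.85 × 0.15/80), about 10.7 points, so the plot would not show a clear trend.

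Table and figure specifications sit in a separate document (SAP section 1), which may hold more detail. These points limit the severity. They do not supply an ESA-status split for TEAEs: starting dose is the only subgroup specified for the overall summary. The clause allowing other endpoints as needed reaches only the listed subgroups, and ESA status is not one of them.

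**Conclusion.** The pooling follows directly from the two dosing tables. Differences across starting doses can therefore reflect cohort mix. For the primary endpoint this is partly offset by other planned analyses; for TEAEs no ESA-status split is specified. The change is worth making, but the issue does not undermine the primary result.

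The 2 to 18 point range is conditional on the assumed 85% converter response, an initiator deficit of 10 to 30 points, a 10% to 40% initiator share, even conversion rows and 80% of initiators under 100 kg. It illustrates what could happen and does not forecast this trial.

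Splitting the cells would not yield clean dose comparisons either. Among converters, starting dose still follows prior ESA dose, and converters moved down by the cap stay in the 100 mg conversion row. What the split removes is the avoidable mixing of cohorts.

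**What to change.** In SAP 9.3, present starting dose within ESA status, as conversion 70, 100 and 150 mg and initiation 70 and 100 mg, with the number of subjects in each cell. Use this for the overall TEAE summary and for the primary-endpoint forest plot. Label it descriptive, and state that starting dose among converters follows prior ESA dose.

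One conflict must be reconciled first, because it defines the levels: Protocol 2.6 names 200 mg among the starting doses obtained from the conversion table, but the tables in both documents stop at 150 mg.

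The cost is one line of text and two more rows; SAP 7.1 already covers starting dose and ESA status. The downside is very wide intervals in the initiation 100 mg row. Under the assumptions above it holds 0.2 × 60 = 12 subjects, with a normal-approximation half-width at 65% of 1.96 × √(0.65 × 0.35/12), about 27 points. With 10% initiators it holds 6, and the half-width is about 38 points. Cell counts make that visible.
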